10.4 Neurophysiological variables

Frequencies (N. %) will be shown for the following qualitative variables:

- Nerve conduction study (EMG)
 - Axonal / Demyelinating (Altered / Unaltered)
- Sudoscan Electrocuteaneous Conductance (ECC):
- RR Interval Variability (Altered / Unaltered)
 - Contingency (descriptive) table of RR interval variability with pre-treatment and follow-up data.

Descriptive statistics (Mean, SD, Median, Minimum, Maximum, Q1, Q3 and N) of the following

quantitative variables will be displayed:

- Nerve conduction study (EMG)
 - Ulnar / peroneal CMAP amplitude (mV)
 - Ulnar / Sural SNAP amplitude (μ V)
- Sudoscan Electrocutaneous Conductance (ECC):
 - Hands result (μ S)
 - Feet result (μ S)
- Change, difference, from values indicated at start of treatment:
 - Ulnar / peroneal CMAP amplitude
 - Ulnar / Sural SNAP amplitude
 - CCE by Sudoscan (hands and feet)

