2. LIST OF ABBREVIATIONS

Abbreviation	Definition
ATTR	Transthyretin Amyloidosis
ATTR-ACT	Tafamidis Treatment Study for Patients with Transthyretin Amyloid Cardiomyopathy
ATTR-CM	Transthyretin cardiac amyloidosis
ATTR-PN	Transthyretin amyloidosis with polyneuropathy
ATTRv	Hereditary transthyretin amyloidosis
ATTRwt	Natural or wild-type transthyretin amyloidosis
CCE	Conductance Cutaneous Electrochemistry
CNS	Central nervous system
COMPASS-31	Composite Autonomic Symptom Score 31
CV	Cardiovascular
CVR-R	Coefficient of Variation of the R-R interval
eGFR	Estimated Glomerular Filtration Rate
EMG	Electromyogram
HF	Heart failure
LTE	ATTR-ACT Long-term Extension Study
mBMI	Modified body mass index
NCS	Nerve conduction studies
NIS	Neuropathy Impairment Score
NIS-LL	Neuropathy Impairment Score Lower Limbs
Norfolk QoL-DN	Norfolk Quality of Life-Diabetic Neuropathy

PFIZER CONFIDENTIAL

PN	Polyneuropathy
PND	Polyneuropathy Disability Score
QoL	Quality of Life
SCR	Sympathocutaneous response
TTR	Transthyretin

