9. RESEARCH METHODS

9.1. Study design

Retrospective, multicenter, non-interventional, observational and descriptive study.

It will by no means interfere with the investigator's decision on the most appropriate medical care or treatment for the patient or carrier.

The variables collected are consistent with the objectives of the study and will be described in more detail in Section 9.3:

Primary objective	Primary variables
To determine the efficacy of tafamidis free acid 61 mg in ATTRv patients with neurologic involvement included in studies B3461028 and/or LTE (B3461045) in Spain through changes in the NIS scale at 12 months.	Neuropathy Impairment Score (NIS)
Secondary objectives	Secondary variables
To determine the efficacy of tafamidis 61 mg in ATTRv patients with neurologic involvement included in studies B3461028 and/or LTE (B3461045) in Spain using additional non-cardiac variables at 6, 12, 18, 24 and 36 months after the start of treatment.	
 - NIS at 6, 18, 24 and 36 months - NIS-LL, Norfolk QoL-DN, COMPASS-31 and FAP-RODs, FAP - % of patients who do not have stage progression in the PND score

PFIZER CONFIDENTIAL

	
 - % of patients responding to treatment (defined as <4p in NIS and <2p in NIS-LL) - R-R Range Variability - mBMI - Amplitude of the potentials measured in sural sensory and ulnar, tibial and peroneal motor NCS

To determine the efficacy of tafamidis free acid 61 mg in ATTRwt patients with neurological symptoms included in studies B3461028 and/or LTE (B3461045) in Spain, through non-cardiac variables at 6, 12, 18, 24 and 36 months after treatment initiation.
	
 - NIS, NIS-LL, Norfolk QoL-DN, COMPASS-31 and FAP-RODs, FAP - % of patients who do not have stage progression in the PND score - % of patients responding to treatment (defined as <4p in NIS and <2p in NIS-LL) - R-R Range Variability - mBMI. - Amplitude of the potentials measured in sural sensory and ulnar, tibial and peroneal motor NCS

To describe the extra-cardiac characteristics of ATTRv and ATTRwt patients included in studies B3461028 and/or LTE (B3461045) in Spain with mixed phenotype treated with tafamidis free acid 61 mg.
	
 - Demographic variables - Age of onset symptoms and at diagnosis - Neurological and extra-cardiac clinical variables

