9.2.1. Inclusion criteria

Patients must meet all of the following inclusion criteria to be eligible for inclusion in the study:

[figure not shown]
1. Be of legal age (>18 years).
2. Have participated in studies B3461028 and/or B3461045 in Spain.
3. Have been treated for at least 12 months with tafamidis free acid 61 mg.
4. Have a minimum of 12 months of neurological follow-up after starting treatment with tafamidis free acid 61 mg and have data from previous neurological evaluation or at the time of starting treatment with tafamidis free acid 61 mg.
5. Have been diagnosed with ATTR amyloidosis polyneuropathy (ATTR-PN), based on any of the following criteria:
 - a. Decreased amplitude in EMG studies, at least two nerves below normal, excluding median, or other nerve entrapment sites.
 - b. A reduction in amplitude by more than 50% by at least two nerves above the patient's baseline value, excluding the median.
 - c. Two different altered fine fiber tests (Sudoscan, CRS, RR interval variability, skin biopsy...).
 - d. A clinic compatible with small fiber neuropathy (painful or dysautonomic) and an altered fine fiber test.

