NIS (Neuropathy Impairment Score) is a clinically important, sensitive measure of individual neurological function, assessing sensory function, reflexes, and muscle weakness			
NIS-LL			
NIS-LL (Neuropathy Impairment Score Lower Limbs) is a clinically important, sensitive measure of neurological function in individuals, assessing sensory function, reflexes, and muscle weakness of the lower limbs			
PND	Result	Medical Record	The investigator will collect the data in the CRF reflecting the information included in the medical record or calculated from the medical record data
PND (Polyneuropathy disability score) is a simple staging system according to the degree of neuropathic dysfunction and its impact on ambulation			
FAP	Result	Medical Record	
FAP (Family Amyloidotic polyneuropathy stage) is a staging system based on symptom severity and disease progression			
NCS (EMG): sural sensory, ulnar, tibial and peroneal nerves	Result	Medical Record	
CCE - Sudoscan (feet and hands)			The investigator will collect the data in the CRF reflecting the information included in the medical record
Electrochemical Cutaneous Conductance allows us to measure autonomic sudomotor function in a non-invasive, rapid and accurate manner			
CVR-R			
The coefficient of variation of the R-R interval is a measure of cardiovascular autonomic dysfunction. It is calculated as the standard deviation percentage of the R-R intervals divided by their mean			

Norfolk QoL-DN	Result	Medical Record	
Norfolk Quality of Life Questionnaire for Diabetic Neuropathy is a standardized and validated instrument that assesses the effect of polyneuropathy on the functionality and quality of life of the individual			
FAP-RODS			The investigator will collect the data in the CRF reflecting the information included in the medical record
FAP-RODS (Familial Amyloid Polyneuropathy Specific Rasch-Built Overall Disability Scale) is a questionnaire that assesses the effect of neuropathy on daily activities	Result	Medical Record	
COMPASS-31			
COMPASS-31 (Composite Autonomic Symptom Score 31) is a questionnaire designed to assess the severity and functional ability in patients with autonomic dysfunction			
Proteinuria			
Albuminuria/microalbuminuria levels	Result	Medical Record	The investigator will collect the data in the CRF reflecting the information included in the medical record
eGFR (estimated Glomerular Filtration Rate)			

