 - change at 24 months from baseline <4p in NIS-LL, patients who have achieved less than 4 points in the NIS-LL at Month 24.
 - change at 36 months from baseline (<12p in NIS and <6p in NIS-LL), patients who

have achieved less than 12 points in the NIS and simultaneously less than 6 points in the NIS-LL at Month 36.

Patients who do not meet the previous condition in each month will be considered non-responders. If complete data is not available, the value will be left as missing.

– **NIS and NIS-LL:** Results will be presented in each month, defining responder as:

- change at 6 months from baseline (<2p in NIS and <1p in NIS-LL), patients who have achieved less than 2 points in the NIS and simultaneously less than 1 point in the NIS-LL at Month 6.
- change at 12 months from baseline (<4p in NIS and <2p in NIS-LL), patients who have achieved less than 4 points in the NIS and simultaneously less than 2 points in the NIS-LL at Month 12.
- change at 18 months from baseline (<6p in NIS and <3p in NIS-LL), patients who have achieved less than 6 points in the NIS and simultaneously less than 3 points in the NIS-LL at Month 18.
- change at 24 months from baseline (<8p in NIS and <4p in NIS-LL), patients who have achieved less than 8 points in the NIS and simultaneously less than 4 points in the NIS-LL at Month 24.
- change at 36 months from baseline (<12p in NIS and <6p in NIS-LL), patients who have achieved less than 12 points in the NIS and simultaneously less than 6 points in the NIS-LL at Month 36.

In this case, patients who do not meet the previous two conditions in each month will be considered non-responders. If complete data is not available (NIS and NIS-LL), the value will be left as missing.

- R-R Range Variability (section 10.4)
- mBMI (section 10.2).
- Amplitude of the potentials measured in sural sensory and ulnar, tibial and peroneal motor NCS (section 10.4)

To the extent possible, parametric (paired t-test) or non-parametric (Wilcoxon) statistical tests will be performed, depending on the sample distribution, to study whether there are differences in the unit change rate for pre- and post-treatment previous numeric variables (total and subgroups).

12.2.2 Secondary objective 2

“To determine the efficacy of Tafamidis free acid 61 mg in ATTRwt patients with neurological symptoms included in studies B3461045 and/or LTE (B3461045) in Spain, through non-cardiac variables at 6, 12, 18, 24 and 36 months after treatment initiation.”

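### R-R variability is a continuous coefficient in the protocol but only Altered/Unaltered in the SAP, so further decline in patients already altered at baseline cannot be shown

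*SAP*

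**What the plan says.** Protocol 9.1 lists "R-R Range Variability" among the secondary variables for both efficacy objectives, ATTRv and ATTRwt. The only operational definition is in the variables table of Protocol 9.3, under CVR-R: "It is calculated as the standard deviation percentage of the R-R intervals divided by their mean". The abbreviation list expands CVR-R as "Coefficient of Variation of the R-R interval". This is a percentage on a continuous scale.

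SAP 9.2 (baseline) and SAP 10.4 (follow-up) place the variable under qualitative variables as "RR Interval Variability (Altered / Unaltered". SAP 10.4 adds one display: "Contingency (descriptive) table of RR interval variability with pre-treatment and follow-up data". SAP 12.2.1 and 12.2.2 add nothing and refer back: "R-R Range Variability (section 10.4".

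Altered R-R variability can also help a patient qualify for the study. Entry criterion 5c in Protocol 9.2.1 reads "Two different altered fine fiber tests (Sudoscan, CRS, RR interval variability, skin biopsy", and 5d reads "A clinic compatible with small fiber neuropathy (painful or dysautonomic) and an altered fine fiber test".

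**The concern.** The hypothesis in Protocol 8 and SAP 3.2 is slower progression of polyneuropathy. An efficacy variable serves that hypothesis only if it can register progression. On a two-level scale, a patient in the worse category at the start has no lower category to move to. Any further loss of R-R variability is tabulated exactly as no change would be.

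There is no control group, so nothing in the design would reveal the loss. A large altered-to-altered count could be reported as stable autonomic function while it contains unmeasured decline. The variable also falls outside the paired analyses in SAP 12.2.1 and 12.2.2, which cover numeric variables only.

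**Working it through.** The documents give no power, precision or sample-size figure for this variable, so there is none to reproduce. The check is a comparison of the texts, followed by a small illustration.

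**Scale and treatment in SAP 10.4**

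| Variable | Altered/Unaltered | Quantitative summary | Change from start of treatment |
|---|---|---|---|
| CMAP and SNAP amplitudes | not for the amplitude itself | yes | yes |
| Sudoscan, hands and feet | no levels given | yes | yes |
| R-R variability | yes | no | no |

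Of these three, R-R variability alone lacks a numeric summary, although the protocol defines it numerically. Neither document gives a cut-off for altered.

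**What the two-level table can show**

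- Unaltered at baseline: stays unaltered, or becomes altered (worsening visible).
- Altered at baseline: stays altered, or becomes unaltered (improvement visible, worsening not).

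For example, take illustrative values of 2.0% at baseline and 0.8% at follow-up, both assumed to be classed as altered. The relative loss is (2.0 − 0.8)/2.0 = 60%, and the patient is entered as altered to altered.

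**How many patients can show worsening**

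Input from SAP 4: n = 10 expected per genotype. Assumption: k patients are altered at baseline, with k not given anywhere and so taken over its full range. The maximum number who can show worsening is n − k.

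| k | 0 | 2 | 4 | 5 | 6 | 8 | 10 |
|---|---|---|---|---|---|---|---|
| n − k | 10 | 8 | 6 | 5 | 4 | 2 | 0 |

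If each patient unaltered at baseline truly crosses with probability q (also assumed), the chance of seeing at least one worsening is 1 − (1 − q)^(n − k). For q = 0.20:

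- k = 0: 1 − 0.8^10 = 0.89
- k = 5: 1 − 0.8^5 = 0.67
- k = 8: 1 − 0.8^2 = 0.36
- k = 10: 0

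At k = 5 the result is 0.41 for q = 0.10 and 0.83 for q = 0.30. With a numeric change, all 10 patients could contribute whatever k is, provided that the values were recorded.

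**Link to entry**

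Criterion 5 is met by any one of a to d. Routes a and b concern nerve amplitudes. R-R variability is one of the tests named in 5c, where two are needed, and could serve as the single test in 5d. Some patients may therefore be altered at baseline. SAP 5 says that the CRF data cannot confirm criterion 5, so the number who entered on this test is not recoverable. The baseline count itself will appear in the SAP 9.2 table.

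**The case against.** Several stronger readings are tempting, and the documents do not support them.

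- A reader might infer that the table will look like stability or benefit whatever happens. It will not: it has an unaltered-to-altered cell, and the blind spot covers only patients altered at baseline.
- A reader might infer that patients were selected as altered at baseline, so that chance return across the cut-off would mimic improvement. Criterion 5 does not require altered R-R variability and sets no date for the qualifying test. The analysis baseline (SAP 9 and 10.3.1) is the latest value from the 12 months before, or at, inclusion in the parent studies. A qualifying test could be later than that.
- A reader might infer from SAP 8.2.3 that these patients have arrhythmia or conduction block. That section only lists them as answer options for the first sign of disease. Where a rhythm disorder is present, a numeric CVR-R would be harder to interpret, which is a fair caution about the remedy.
- A reader might infer a breach of the protocol. Protocol 9.7 lets the SAP modify the plans and calls for an amendment only for major changes to primary endpoints or their analyses.

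The stronger defence concerns importance and feasibility. This is one of many secondary variables in a study described as descriptive, with NIS as the primary variable. Autonomic function is also followed by COMPASS-31 and by Sudoscan, both numeric. The data are retrospective, Protocol 9.9 admits that follow-up data may be scarce, and the CRF is not among the documents. If it holds only the two levels, the SAP summary simply follows what was captured. All of this stands. It limits the weight of the point and makes the fix conditional, but it does not restore the information lost by using two levels.

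**Conclusion.** The point holds as a loss of information on one secondary efficacy variable. The SAP replaces the protocol's continuous definition with two levels and gives no reason. For patients altered at baseline, observable worsening is zero by construction; for the others it remains observable.

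The size depends on k, which the documents do not give. Across the whole range, between 10 and 0 of the 10 expected patients per genotype can show worsening. The probabilities above also rest on assumed crossing rates and are illustrations only. The conclusion takes the variable named in Protocol 9.1 to be the CVR-R defined in 9.3, the only definition offered. The primary analysis is unaffected. This is a worthwhile, low-cost improvement.

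**What to change.** 1. Where numeric values are recorded, add CVR-R (%) to the quantitative variables in SAP 9.2 and 10.4 and to the 10.4 list of changes from start of treatment, and state N with numeric data at each time point. This brings it into the numeric analyses of secondary objectives 1 and 2. Assign visits as for the amplitudes and Sudoscan.
2. Keep the Altered/Unaltered table as a supplement. Report worsening with patients unaltered at baseline as the denominator, say how altered was determined, and state that altered-to-altered is not evidence of stability.
3. If the CRF holds only the two levels, add the numeric value from existing test reports where available. Failing that, state the departure from the protocol definition and confine the conclusion to what the two levels can show.

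The cost is SAP wording if the numbers are already captured. If not, it is one extra CRF field and some re-abstraction at the sites. In either case N may be smaller for the numeric summary, because some reports may lack the value.

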10.5 Scales

See Section 6.1.1 for numerical reassignment of visits.

10.5.1 Norfolk QoL-DN (Norfolk Quality of Life-Diabetic Neuropathy)

Descriptive statistics (Mean, SD, Median, Minimum, Maximum, Q1, Q3 and N) of the following quantitative variable will be shown:

- Norfolk QoL-DN result (value assigned at each visit).
- Increase for each visit (monthly unit change x month).
- To the extent possible, parametric (paired t-test) or non-parametric (Wilcoxon) statistical tests will be performed, depending on the sample distribution, to study whether there are differences in the unit change rate for pre- and post-treatment Norfolk QoL-DN (total and subgroups).

10.5.2 FAP-RODS (Familial Amyloid Polyneuropathy Specific Rasch-Built Overall Disability Scale)

Descriptive statistics (Mean, SD, Median, Minimum, Maximum, Q1, Q3 and N) of the following quantitative variable will be shown:

- FAP-RODS result (total score ranges from 0 to 68) (0=Lower ability to perform daily activities and 68=Greater ability to perform daily activities) (value assigned at each visit).
- Increase for each visit (monthly unit change x month).
- To the extent possible, parametric (paired t-test) or non-parametric (Wilcoxon) statistical tests will be performed, depending on the sample distribution, to study whether there are differences in the unit change rate for pre- and post-treatment Norfolk QoL-DN (total and subgroups).

10.5.3 Composite Autonomic Symptom Score 31 (COMPASS-31) autonomic symptoms questionnaire

Descriptive statistics (Mean, SD, Median, Minimum, Maximum, Q1, Q3 and N) of the following quantitative variable will be shown:

- COMPASS-31 result (total score ranges from 0 to 100) (0=Lesser severity of dysautonomia and 100=Greater severity of dysautonomia) (value assigned at each visit).
- Increase for each visit (monthly unit change x month).
- To the extent possible, parametric (paired t-test) or non-parametric (Wilcoxon) statistical tests will be performed, depending on the sample distribution, to study whether there are differences in the unit change rate for pre- and post-treatment COMPASS-31 (total and subgroups).

10.6 Renal Assessment Variables

Frequencies (N. %) will be shown for the following qualitative variables:

- Proteinuria (Yes / No)
- Albumin/Microalbuminuria (Yes / No)

Descriptive statistics (Mean, SD, Median, Minimum, Maximum, Q1, Q3 and N) of the following quantitative variables will be displayed:

- Proteinuria result (g/24h)
- Albumin / microalbuminuria result (mg/g)
- Estimated glomerular filtration rate (eGFR) (mL/min/1.73m²)

10.7 Ophthalmologic Assessment Variables

Descriptive statistics (Mean, SD, Median, Minimum, Maximum, Q1, Q3 and N) of the following quantitative variable will be shown:

- Intraocular Pressure result (mmHg)

Frequencies (N. %) will be shown for the following qualitative variable:

- Grading of Vitreous Opacity (Altered / Unaltered)

11 ADVERSE EVENTS

Analyses will be performed on the total population and subgroup based on genotype (ATTRv and ATTRwt). Descriptive analyses will be presented with no comparisons between genotype groups.

11.1 Adverse events total

The categorical variables to be described (n. %) are:

- Number of patients with at least one adverse event

A listing of adverse events with the main variables will be shown.

11.2 Serious Adverse Events

The categorical variables to be described (n. %) are:

- Number of patients with at least one serious adverse event

A listing of serious adverse events with the main variables will be shown.

11.3 Related Adverse Events

The categorical variables to be described (n. %) are:

- Number of patients with at least one related adverse event related to a Pfizer drug

A listing will be shown with the main variables of adverse events related to a Pfizer drug (specifying the corresponding treatment).

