Tafamidis is a benzoxazole derivative without nonsteroidal anti-inflammatory activity that binds to TTR thyroxine binding sites with high affinity and selectivity. This leads to inhibition of dissociation of TTR tetramer into monomers, preventing the formation of amyloid fibers ([Bulawa CE, et al](#))¹⁴. Tafamidis 20 mg has been shown to slow the progression of peripheral neurological deterioration in patients with ATTR polyneuropathies (ATTR-PN) at stage 1 ([Coelho T, et al](#))¹⁵ and has been approved in Spain since 2011 for the treatment of transthyretin amyloidosis in adult patients with stage 1 polyneuropathy to delay peripheral neurological impairment (Information available on [AEMPS](#))¹⁶.

In the clinical trial to evaluate the safety and efficacy of tafamidis in transthyretin cardiac amyloidosis (ATTR-ACT), tafamidis at a dose of 20 mg and 80 mg (4 x 20 mg) was shown (compared to placebo) to reduce the combination of all-cause mortality and the frequency of cardiovascular-related (CV) hospitalizations, as well as to slow down the decline in functional capacity and quality of life (QoL) of patients with ATTR-CM of hereditary origin or wt ([Maurer MS, et al](#))¹⁷. Based on these outcomes, tafamidis obtained FDA and EMA approval for the treatment of patients with ATTR-CM (Information available at: [AEMPS; FDA](#))^{18,19}.

Upon completion of the ATTR-ACT study, patients had the option to participate in the extension study, LTE ([NCT02791230](#))²⁰ (B3461045), in which patients could be treated with tafamidis for an additional 60 months ([Damy T, et al](#))²¹. In the LTE, patients who in the ATTR-ACT study received tafamidis continued to receive the same dose, while patients who received placebo were randomly reassigned to receive tafamidis 80 mg or 20 mg at a 2:1 ratio. Following the July 20, 2018 protocol addendum, all patients were switched to 61 mg of tafamidis free acid, a new single capsule formulation that is bioequivalent to 80 mg of tafamidis meglumine used in the ATTR-ACT ([Lockwook PA, et al](#))²². Published outcomes show that tafamidis 80 mg/61 mg has greater efficacy by reducing all-cause mortality by 30% versus tafamidis 20 mg ([Damy T, et al](#))²⁰.

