9.3. Variables

The variables to be collected from each patient at participating sites will be:

- Clinical parameters available in their medical history in the 12 months prior to their inclusion in studies B3461028 and/or LTE (B3461045).
- Clinical parameters available in their medical history at the time of inclusion in studies B3461028 and/or LTE (B3461045) (last visit to the site before inclusion in the study).
- Routine follow-up visits (up to the last available visit prior to enrollment in the TRAMA study).

The variables to be collected from each individual's medical history during the course of this study will be:

- **Treatment-related variables:**

- Date of consent signature for entry into study B3461028 and B3461045
- ATTR Treatment Start Date:
 - Initiation of treatment with commercial medication (tafamidis 20 mg)
 - Treatment regimen in the trial of ATTR-ACT or LTE tafamidis 20 mg
 - Treatment regimen in the ATTR-ACT or LTE tafamidis 80 mg or 61 mg trial
- Patient is currently on treatment with tafamidis free acid 61 mg (if not, specify stop date)

- **Demographic variables:**

[figure not shown]
- Age, gender
- Genotype: mutations (homozygosity/heterozygosity) or wt
- Age of disease onset (in order to characterize whether the disease onset was neurological or cardiological and to understand why it was not treated with available therapeutic options)
- First disease-related sign or symptom
- Age at disease diagnosis

- **Variables collected at each follow-up visit:**

- **Extra-cardiac 'red flags' medical history:**

- Carpal tunnel syndrome (if yes, if there was a surgery/date)
 - Lumbar stenosis
 - Gastrointestinal disturbances: diarrhea/constipation, early satiety

PFIZER CONFIDENTIAL

- Urological disturbances: urinary tract infections, urinary incontinence, urinary infections, incomplete emptying sensation
- Ophthalmological disturbances
- Central nervous system (CNS) disturbances (seizures, stroke or transient ischemic attack, cognitive impairment)
- Symptoms of autonomic neuropathy: impaired sweating, sexual dysfunction, orthostatic hypotension
- Symptoms of peripheral neuropathy (allodynia, paresthesia, hyperalgesia...)
- Unintentional weight loss

- Modified Body Mass Index (mBMI)
- Neurological variables:
 - NIS (*Neuropathy Impairment Score*)
 - NIS-LL (*Neuropathy Impairment Score Lower Limbs*)
 - PND (*Polyneuropathy disability score*)
 - FAP (*Family Amyloidotic polyneuropathy stage*)
- Neurophysiological variables:

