11. MANAGEMENT AND REPORTING OF ADVERSE EVENTS/ADVERSE REACTIONS

This study protocol requires human review of patient-level unstructured data; unstructured data refer to verbatim medical data, including text-based descriptions and visual depictions of medical information, such as medical records, images of physician notes, neurological scans, X-rays, or narrative fields in a database. The reviewer is obligated to report adverse events (AEs) with explicit attribution to any Pfizer drug that appear in the reviewed information (defined per the patient population and study period specified in the protocol). Explicit attribution is not inferred by a temporal relationship between drug administration and an AE, but must be based on a definite statement of causality by a healthcare provider linking drug administration to the AE.

The requirements for reporting safety events on the non-interventional study (NIS) adverse event monitoring (AEM) Report Form to Pfizer Safety are as follows:

PFIZER CONFIDENTIAL

- All serious and non-serious AEs with explicit attribution to **any Pfizer drug** that appear in the reviewed information must be recorded on the case report Form and reported, within 24 hours of awareness, to Pfizer Safety using the NIS AEM Report Form.
- Scenarios involving drug exposure, including exposure during pregnancy, exposure during breast feeding, medication error, overdose, misuse, extravasation, lack of efficacy, and occupational exposure associated with the use of a Pfizer product must be reported, within 24 hours of awareness, to Pfizer Safety using the NIS AEM Report Form.

For these AEs with an explicit attribution or scenarios involving exposure to a Pfizer product, the safety information identified in the unstructured data reviewed is captured in the Event Narrative section of the report form, and constitutes all clinical information known regarding these AEs. No follow-up on related AEs will be conducted.

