8.1.1 ATTR Treatment Start Date

Frequencies (N. %) will be shown for the following qualitative variables:

- Commercial medication (Tafamidis 20 mg) (Yes / No)
- Treatment regimen in ATTR-ACT (B3461028) or LTE (B341045) trial of origin (multiple choice table):
 - ATTR-ACT or LTE Tafamidis 20 mg
 - ATTR-ACT or LTE Tafamidis 80 mg
 - ATTR-ACT or LTE Tafamidis 61 mg
- Is the patient currently on Tafamidis free acid 61 mg? (Yes / No)

Descriptive statistics (Mean, SD, Median, Minimum, Maximum, Q1, Q3 and N) of the following quantitative variables will be displayed:

- Duration for the following treatments (in months):
 - ATTR-ACT or LTE Tafamidis 20 mg, calculated as end date - start date.
 - ATTR-ACT or LTE Tafamidis 80 mg, calculated as end date - start date.
 - ATTR-ACT or LTE Tafamidis 61 mg, calculated as end date - start date. If still on treatment, up to the enrollment date will be considered (enrollment date - start date).

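### SAP 11.1–11.3 count adverse events without regard to product or regimen at onset, so the related-event percentage cannot be read as a tafamidis 80/61 mg result

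*SAP*

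**What the plan says.** SAP section 11 plans three counts, each with a listing: in 11.1 the "Number of patients with at least one adverse event", in 11.2 the "Number of patients with at least one serious adverse event", and in 11.3 the "Number of patients with at least one related adverse event related to a Pfizer drug". They are shown for the total population and by genotype, with no comparison between genotypes. The 11.3 listing is to state the treatment concerned. Section 11 gives no onset window and no rule for assigning an event to a regimen.

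Protocol section 11 governs what is recorded: "All serious and non-serious AEs with explicit attribution to" any Pfizer drug, where these appear in the reviewed information. Attribution must rest on a definite causality statement by a healthcare provider, and timing alone is not enough. The section also refers to a study period specified in the protocol.

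Protocol 9.3 collects clinical data from the 12 months before inclusion in B3461028 and/or the LTE up to the last available visit before TRAMA enrolment. It also records commercial 20 mg and the trial regimens. Protocol section 7 gives the history of trial treatment: ATTR-ACT used placebo, 20 mg and 80 mg. In the LTE, "patients who received placebo were randomly reassigned to receive tafamidis 80 mg or 20 mg at a 2:1 ratio", and all patients moved to 61 mg after the July 2018 addendum. SAP 8.1.1 lists commercial 20 mg (yes/no) and trial regimens of 20, 80 and 61 mg. It has no placebo category.

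**The concern.** Every objective names tafamidis 61 mg, and the efficacy tables are anchored to the start of treatment. The safety tables have no such anchor. A reader of the report will naturally take the related-event percentage as the proportion of patients with a drug-related event on 61 mg. As defined, the figure pools different tafamidis doses and can include events attributed to unrelated Pfizer medicines. The groups are small, so one misplaced patient visibly changes the percentage. If prior exposure differs between ATTRv and ATTRwt patients, the two columns printed side by side can differ for that reason alone.

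**Working it through.** The documents state no adverse event rate, so there is no planned figure to reproduce. The check compares the counting rule with what the records can contain, then works out the effect of one patient.

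**1. What can pass the 11.3 rule.** The rule needs an explicit attribution to a Pfizer drug and nothing more.

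| Event in the reviewed record | Counted in 11.3? |
|---|---|
| Attributed to tafamidis, onset on 80 or 61 mg | Yes |
| Attributed to tafamidis, onset on commercial or trial 20 mg | Yes |
| Attributed to another Pfizer product, at any time | Yes |
| Onset on placebo, attributed to study drug | Yes, if the provider made that attribution |
| Onset before any tafamidis | Only through another Pfizer product |
| No explicit attribution | No |

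Rows two to five are the events at issue. Protocol section 11 requires only attributed events on the case report form, so 11.1 and 11.2 draw on the same pool and share the problem.

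**2. Effect on the percentage.** The measure is patients with at least one event. Let *a* be patients with at least one qualifying event on 80/61 mg, *b* patients counted only for an event from rows two to five, and *n* the group size.

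- Reported percentage = 100 × (a + b)/n.
- Percentage on study drug = 100 × a/n.
- Excess = 100 × b/n.

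SAP section 4 expects 10 ATTRv and 10 ATTRwt patients, 20 in total.

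| b | Excess, n = 10 | Excess, n = 20 |
|---|---|---|
| 1 | 10 points | 5 points |
| 2 | 20 points | 10 points |
| 3 | 30 points | 15 points |

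A patient who has both an outside event and a qualifying event is already in *a* and adds nothing.

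**3. Chance that b is at least 1.** The documents give no basis for this, so *p* below is an assumption: the probability that a given patient is counted only for an outside event. With independent patients, P(b ≥ 1) = 1 − (1 − p)^n.

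| Assumed p | n = 10 | n = 20 |
|---|---|---|
| 5% | 1 − 0.95^10 = 40% | 1 − 0.95^20 = 64% |
| 10% | 1 − 0.90^10 = 65% | 1 − 0.90^20 = 88% |
| 20% | 1 − 0.80^10 = 89% | 1 − 0.80^20 = 99% |

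Even a small assumed probability makes it fairly likely that at least one patient in a genotype group is counted this way.

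**The case against.** The case for leaving the section alone has four parts.

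- **Safety is not an objective.** Protocol section 11 is a pharmacovigilance duty covering all the sponsor's products, and SAP 11.3 mirrors it. This stands as a reason to rate the point as moderate. It does not explain why a percentage in a 61 mg report should pool products: reporting duties are met by recording and listing the events.
- **The attribution filter is strict.** This also stands. A reader might infer that any event before treatment or on placebo is counted. The documents do not support that, because an explicit causal statement is needed. The filter does not stop events attributed to 20 mg or to another Pfizer product.
- **The listing names the treatment.** With about 20 patients a reader could recount by hand, so this is a partial remedy. But the SAP does not say that the listing shows dose or onset date, and the printed percentage stays as it is.
- **A study period is mentioned.** The milestones are redacted and may define one. A calendar period would still not separate products or regimens.

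Two further readings are tempting and should not be drawn. One is that the share of reviewed months before 61 mg measures how many counted events are misplaced. Share of time is not share of events, and the documents give neither the months per patient nor the event rates. The other is that every outside event shifts the percentage. Only a patient counted solely for such an event does.

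**Conclusion.** The point holds for the counting rule. As written, the n (%) in SAP 11.1–11.3 cannot be read as tafamidis 80/61 mg results, because neither the product nor the regimen at onset enters the definition. Each patient counted only for an outside event adds 10 points to a genotype percentage and 5 to the total. This rests on the SAP's expected numbers; with *n* evaluable patients the shift is 100/n. How many patients will be affected cannot be known from the documents, and the number may be zero. The change is worth making before the tables are produced. It does not affect the efficacy objectives.

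**What to change.** In SAP section 11:

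1. Keep the listing of events related to any Pfizer drug, and state that it shows product, regimen at onset and onset date.
2. Give the n (%) in 11.1–11.3 separately for events attributed to tafamidis and events attributed to other Pfizer products.
3. Split the tafamidis events by regimen at onset: before 80/61 mg (including 20 mg and blinded or placebo periods), 80 mg, and 61 mg. Derive this from the recorded treatment dates and event onset, using month and year where nothing finer is known. One pooled early row is enough, because the documents do not show that placebo dates are collected.
4. Label the 80/61 mg rows as the study-drug result. This matches SAP section 5, which accepts either 80 or 61 mg dates when it checks eligibility.
5. State that a patient may appear in more than one row, so the rows need not add up.

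A person-time rate is optional. If one is added, end the denominator at the last reviewed visit. The 61 mg duration in SAP 8.1.1 runs to enrolment for patients still on treatment, which can include time after the last visit reviewed.

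The cost is SAP wording, one derived variable and a few more table rows. The study-drug row will show a smaller count than the pooled figure, but no event is lost from the report.
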